## 3.9.2 Guidelines for Use of CYP Inhibiting/Inducing Drugs

At the systemic exposure levels expected in this study, acalabrutinib inhibition of CYP metabolism is not anticipated. However, as discussed in Section 1.4.1, concomitant administration of acalabrutinib with a strong CYP3A inhibitor increased exposure by approximately 5-fold. Conversely, concomitant administration of acalabrutinib with a strong CYP3A inducer has the potential to decrease acalabrutinib exposure and could reduce efficacy. Consequently, the concomitant use of strong inhibitors or inducers of CYP3A (see Appendix 2) should be avoided when possible. If a subject requires treatment with a strong/moderate CYP3A inhibitor or strong CYP3A inducer while on-study, follow the acalabrutinib treatment/dosing instructions described in Section 3.10.7 and monitor the subject closely for potential toxicities.

## 3.9.3 Guideline for Use of Drugs that Affect Gastric pH

The effect of agents that reduce gastric acidity (e.g., antacids or proton-pump inhibitors) on acalabrutinib absorption was evaluated in a healthy volunteer study (ACE-HV-004). Results from this completed study indicate that subjects should avoid the use of calcium carbonate containing drugs or supplements for a period of at least 2 hours before and at least 2 hours after taking acalabrutinib.

Use of omeprazole, esomeprazole, lansoprazole or any other proton pump inhibitors while taking acalabrutinib is not recommended due to a potential decrease in study drug exposure. However, the decision to treat with proton-pump inhibitors during the study is at the investigator's discretion, with an understanding of the potential benefit to the subject's gastrointestinal condition and a potential risk of decreased exposure to acalabrutinib.

Although the effect of H2-receptor antagonists (such as famotidine or ranitidine) on acalabrutinib absorption has not been evaluated, if treatment with an H2-receptor antagonist is required, the H2-receptor antagonist should be taken approximately 2 hours after an acalabrutinib dose.

## 3.9.4 Prohibited or Restricted Concomitant Therapy

Any chemotherapy, anticancer immunotherapy, corticosteroids (at dosages equivalent to prednisone >20 mg/day), warfarin or equivalent vitamin K antagonists (e.g., phenprocoumon), experimental therapy, and radiotherapy are prohibited.

At study entry, subjects may be using topical or inhaled corticosteroids or low-dose steroids (≤10 mg of prednisone or equivalent per day) as therapy for comorbid conditions but use of corticosteroids as therapy of the lymphoid cancer is not permitted. During study participation, subjects may also receive systemic or enteric corticosteroids at any required dosage as needed for treatment-emergent immune-mediated adverse reactions associated with pembrolizumab therapy (see Section 3.8).

Live vaccines within 30 days before the first dose of trial treatment and while participating in the trial are prohibited. Examples of live vaccines include, but are not limited to, the following: measles, mumps, rubella, chicken pox, yellow fever, rabies, BCG, and typhoid (oral) vaccine. Seasonal influenza vaccines for injection are generally killed virus vaccines and are allowed. However, intranasal influenza vaccines (e.g., FLUMIST®) are live attenuated vaccines and are not allowed.

Use of calcium carbonate-containing drugs or supplements and short-acting H2-receptor antagonists should be avoided for at least 2 hours before or after acalabrutinib administration (see Section 3.10.7).For additional information on drugs with potential drug-drug interactions, refer to Section 3.10.7.

## 3.10 RISKS ASSOCIATED WITH STUDY TREATMENT

## 3.10.1 Risks Associated with Acalabrutinib

The following summarizes the experience with acalabrutinib in hematological cancer studies. Full details regarding the clinical safety of acalabrutinib are presented in the acalabrutinib IB.

## 3.10.1.1 Contraindications

No contraindications are known for acalabrutinib.

## 3.10.1.2 Warnings and Precautions

#### • Hemorrhage

Serious hemorrhagic events, including fatal events, have occurred in clinical trials with acalabrutinib.

Subjects receiving antithrombotic agents may be at increased risk of hemorrhage. Use caution with antithrombotic agents and consider additional monitoring for signs of bleeding when concomitant use is medically necessary. As a precaution, it is suggested that acalabrutinib be withheld for at least 3 days pre- and post-surgery (see Section 3.10.8).

Subjects with hemorrhage should be managed per institutional guidelines with supportive care and diagnostic evaluations or as clinically indicated.

• Infections

Serious infections (bacterial, viral, and fungal), including fatal events, have occurred in clinical studies with acalabrutinib. The most frequent reported Grade ≥3 infection was pneumonia (preferred term). Consider prophylaxis in subjects who are at increased risk for opportunistic infections. Consider prophylaxis in subjects who are at increased risk for opportunistic infections. Subjects should be monitored for signs and symptoms of infection and treated as medically appropriate.

HBV reactivation and progressive multifocal leukoencephalopathy (PML) have occurred in clinical studies with acalabrutinib; see Section 3.10.5 and Section 4.1.14 for additional information and monitoring guidance for viral hepatitis, and see Section 3.10.3 for additional information and management guidance for signs and symptoms of PML.

#### • Cytopenias

Treatment-emergent Grade 3 or 4 cytopenias, including neutropenia, anemia, and thrombocytopenia, have occurred in clinical studies with acalabrutinib. Blood counts should be monitored as specified in the Schedule of Assessments (Appendix 5 and Appendix 6) and as medically appropriate. Refer to Section 3.8 for study drug modification guidance. Subjects with cytopenias should be managed according to institutional guidelines with maximal supportive care and diagnostic evaluations as clinically indicated.

### Second Primary Malignancies

Second primary malignancies, including solid tumors and skin cancers, have been reported in patients treated with acalabrutinib. The most frequent second primary malignancy was skin cancer (basal cell carcinoma). Subjects should be monitored for signs and symptoms of malignancy. Subjects who develop a second primary malignancy should be managed according to institutional guidelines with diagnostic

evaluations as clinically indicated, and it may be necessary for subjects to permanently discontinue study treatment. Continuation of acalabrutinib treatment should be discussed with the medical monitor. Please refer to Section 6.2.3 for second primary malignancy reporting guidance.

#### Atrial Fibrillation

Atrial fibrillation or flutter have occurred in clinical studies with acalabrutinib, particularly in subjects with cardiac risk factors, hypertension, diabetes mellitus, acute infections, and a previous history of atrial fibrillation. Monitor for symptoms of atrial fibrillation and atrial flutter (e.g., palpitations, dizziness, syncope, chest pain, dyspnea) and obtain an ECG as appropriate. Subjects with atrial fibrillation should be managed per institutional guidelines with supportive care and diagnostic evaluation as clinically indicated.

### 3.10.2 Risks Associated with Pembrolizumab

The following summarizes significant risks with pembrolizumab based on KEYTRUDA Prescribing Information Contraindications and Warnings & Precautions. For additional information, please refer to the KEYTRUDA Prescribing Information.

## 3.10.2.1 Contraindications

No contraindications are known for pembrolizumab.

### 3.10.2.2 Warnings and Precautions

### • Immune-Mediated Pneumonitis

Pembrolizumab can cause immune-mediated pneumonitis, including fatal cases. Monitor subjects for signs and symptoms of pneumonitis. Evaluate subjects with suspected pneumonitis with radiographic imaging and follow the treatment guidance in Section 3.8.3.

#### • Immune-Mediated Colitis

Pembrolizumab can cause immune-mediated colitis. Monitor subjects for signs and symptoms of colitis and follow the treatment guidance in Section 3.8.3.

#### • Immune-Mediated Hepatitis

Pembrolizumab can cause immune-mediated hepatitis. Monitor subjects for changes in liver function and follow the treatment guidance in Section 3.8.3.

#### Immune-Mediated Endocrinopathies

- Hypophysitis: Pembrolizumab can cause hypophysitis. Monitor subjects for signs and symptoms of hypophysitis (including hypopituitarism and adrenal insufficiency) and follow the treatment guidance in Section 3.8.3.
- Thyroid disorders: Pembrolizumab can cause thyroid disorders, including hyperthyroidism, hypothyroidism and thyroiditis. Monitor subjects for changes in thyroid function (at the start of treatment, periodically during treatment, and as indicated based on clinical evaluation) and for clinical signs and symptoms of thyroid disorders, and follow the treatment guidance in Section 3.8.3.
- Type 1 diabetes mellitus: Pembrolizumab can cause type 1 diabetes mellitus, including diabetic ketoacidosis. Monitor subjects for hyperglycemia or other signs and symptoms of diabetes and follow the treatment guidance in Section 3.8.3.

#### Immune-Mediated Nephritis and Renal Dysfunction

Pembrolizumab can cause immune-mediated nephritis. Monitor subjects for changes in renal function and follow the treatment guidance in Section 3.8.3.

#### Immune-Mediated Skin Adverse Reactions

Immune-mediated rashes, including Stevens-Johnson syndrome, toxic epidermal necrolysis (some cases with fatal outcome), exfoliative dermatitis, and bullous pemphigoid can occur. Monitor subjects for suspected severe skin reactions and exclude other causes. Based on the severity of the adverse reaction, withhold or permanently discontinue pembrolizumab and administer corticosteroids. For signs or symptoms of Stevens-Johnson syndrome or toxic epidermal necrolysis, withhold pembrolizumab and refer the subject for specialized care for assessment and treatment. If Stevens-Johnson syndrome or toxic epidermal necrolysis is confirmed, permanently discontinue pembrolizumab.

#### Other Immune-Mediated Adverse Reactions

Immune-mediated adverse reactions, which may be severe or fatal, can occur in any organ system or tissue in patients receiving pembrolizumab. While immune-mediated adverse reactions usually occur during treatment with PD-1/PD-L1 blocking antibodies, they may occur after discontinuation of treatment. For suspected immune-mediated adverse reactions, ensure adequate evaluation to confirm etiology or exclude other causes. Based on the severity of the adverse reaction, withhold pembrolizumab and administer corticosteroids. Upon improvement to Grade 1 or less, initiate corticosteroid

taper and continue to taper over at least 1 month. Based on limited data from clinical studies in subjects whose immune-related adverse reactions could not be controlled with corticosteroid use, administration of other systemic immunosuppressants can be considered. Resume pembrolizumab when the immune-mediated adverse reaction remains at Grade 1 or less following corticosteroid taper. Permanently discontinue pembrolizumab for any Grade 3 immune-mediated adverse reaction that recurs and for any life-threatening immune-mediated adverse reaction. In organ transplant recipients, consider the benefit of treatment with pembrolizumab versus the risk of possible organ rejection.

#### • Infusion-Related Reactions

Pembrolizumab can cause severe or life-threatening infusion-related reactions, including hypersensitivity and anaphylaxis. Monitor subjects for signs and symptoms of infusion-related reactions including rigors, chills, wheezing, pruritus, flushing, rash, hypotension, hypoxemia, and fever. Follow the treatment guidance in Section 3.8.3.

#### • Complications of Allogeneic HSCT

*Allogeneic HSCT after treatment with pembrolizumab*: Immune-mediated complications, including fatal events, occurred in patients who underwent HSCT after being treated with pembrolizumab. Monitor for hepatic veno-occlusive disease, Grade 3 or 4 acute graft-versus-host disease (GVHD) including hyperacute GVHD, steroid-requiring febrile syndrome, and other immune-mediated adverse reactions. Transplant-related mortality has occurred.

Allogeneic HSCT prior to treatment with pembrolizumab: In patients with a history of allogeneic HSCT, acute GVHD, including fatal GVHD, has been reported after treatment with pembrolizumab. Patients who experienced GVHD after their transplant procedure may be at increased risk for GVHD after treatment with pembrolizumab. In subjects with a history of allogeneic HSCT, consider the benefit of treatment with pembrolizumab versus the risk of GVHD.

• Increased Mortality in Patients with Multiple Myeloma When Pembrolizumab is Added to a Thalidomide Analogue and Dexamethasone

Treatment of subjects with multiple myeloma with a PD-1 or PD-L1 blocking antibody in combination with a thalidomide analogue plus dexamethasone is not recommended outside of controlled clinical trials.

#### • Embryo-Fetal Toxicity

Based on its mechanism of action, pembrolizumab can cause fetal harm when administered to a pregnant woman. Advise women of reproductive potential of the potential risk to a fetus and to use effective method of contraception during treatment and for 120 days after the last dose of pembrolizumab (see Section 3.10.9).

# 3.10.3 **Progressive Multifocal Leukoencephalopathy**

Cases of PML have occurred in clinical studies with acalabrutinib. Signs and symptoms of PML may include cognitive and behavioral changes, language disturbances, visual disturbances, sensory deficits, weakness, and coordination and gait difficulties. If PML is suspected, hold further treatment with acalabrutinib until PML is excluded. A diagnostic evaluation may include (but is not limited to):

- Neurologic consultation
- Brain magnetic resonance imaging (MRI)
- PCR analysis for JC virus DNA in cerebrospinal fluid

If PML is confirmed, permanently discontinue acalabrutinib.

# 3.10.4 Transaminase Elevations for Acalabrutinib in Combination with Pembrolizumab

Serum transaminase elevations (including elevations of AST and/or ALT) may be increased in severity and frequency in subjects exposed to the combination of acalabrutinib and pembrolizumab, as compared with subjects exposed to pembrolizumab monotherapy and subjects exposed to acalabrutinib monotherapy. Routine monitoring for serum transaminase elevations must follow the Schedule of Assessments (serum chemistry laboratory assessments in Appendix 5 and Appendix 6). Dosing delays and modifications for subjects with serum transaminase elevations must follow guidance provided in Section 3.8.

# 3.10.5 Hepatitis B Reactivation

Cases of hepatitis B virus (HBV) reactivation have occurred in clinical studies with acalabrutinib. Therefore, subjects with a history of HBV infection should be monitored every 3 months with a quantitative PCR test for HBV DNA. Monitoring every 3 months should continue until 12 months after the last dose of acalabrutinib. Any subject with a rising viral load (above lower limit of detection) should discontinue study drug and have antiviral therapy instituted and a consultation

with a physician with expertise in managing hepatitis B. Insufficient data exist regarding the safety of resuming acalabrutinib in subjects who develop HBV reactivation.

# 3.10.6 Dietary Restrictions

Acalabrutinib can be taken with or without food. Because acalabrutinib is metabolized by CYP3A, subjects should be strongly cautioned against excessive consumption of grapefruit, grapefruit juice, or Seville orange juice (which contain potent CYP3A inhibitors) or using herbal remedies or dietary supplements (in particular, St John's wort, which is a potent CYP3A inducer).

Otherwise subjects should maintain a normal diet unless modifications are required to manage an AE such as diarrhea, nausea, or vomiting.

# 3.10.7 Drug-Drug Interactions

At the systemic exposure levels expected in this study, acalabrutinib inhibition of CYP metabolism is not anticipated. However, acalabrutinib is metabolized by CYP3A. Concomitant administration of acalabrutinib with a strong CYP3A and P-glycoprotein (P-gp) inhibitor, itraconazole increased exposure by approximately 5-fold. Conversely, concomitant administration of acalabrutinib with a strong CYP3A inducer, rifampin, decreases acalabrutinib exposure and could reduce efficacy. Consequently, the concomitant use of strong inhibitors/inducers of CYP3A (see Appendix 2) should be avoided when possible.

If a subject requires short-term treatment with a strong or moderate CYP3A inhibitor (such as anti-infectives for up to 7 days), interrupt acalabrutinib treatment.

If a subject requires treatment with a strong CYP3A inducer, increase the acalabrutinib dose to 200 mg BID during concomitant administration with the strong inducer and return to recommended dose of 100 mg BID after stopping the strong CYP3A inducer. See Appendix 2 for a list of strong CYP3A inhibitors/inducers.

Based on these considerations, subjects who require therapy with drugs listed in Appendix 2 should not be enrolled into the study. If medically justified, subjects may be enrolled if such inhibitors or inducers can be discontinued or alternative drugs that do not affect these enzymes can be substituted within 7 days before first dose of study drug. If a subject requires a strong CYP3A inhibitor while on study, monitor the subject closely for potential drug-related toxicities.

The effect of agents that reduce gastric acidity (e.g., antacids or proton-pump inhibitors,) on acalabrutinib absorption was evaluated in a healthy volunteer study (ACE-HV-004). Results

from this completed study suggest subjects should avoid the use of calcium carbonatecontaining drugs or supplements for a period of at least 2 hours before and at least 2 hours after taking acalabrutinib.

Use of omeprazole, lansoprazole or esomeprazole or any other proton-pump inhibitors while taking acalabrutinib is not recommended due to a potential decrease in study drug exposure. However, the decision to treat with proton-pump inhibitors during the study is at the investigator's discretion, with an understanding of the potential benefit to the subject's gastrointestinal condition and a potential risk of decreased exposure to acalabrutinib.

Although the effect of H2-receptor antagonists (such as famotidine or ranitidine) on acalabrutinib absorption has not been evaluated, if treatment with an H2-receptor antagonist is required, the H2-receptor antagonist should be taken approximately 2 hours after an acalabrutinib dose.

No formal PK drug interaction studies have been conducted with pembrolizumab.

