## 3.2 RATIONALE FOR STUDY DESIGN AND DOSING REGIMEN

As described in Section 1.4, acalabrutinib is currently being evaluated in a Phase 1/2 study in subjects with CLL (ACE-CL-001). In this study, subjects have received oral dosages of 100 to 400 mg QD and 100 to 200 mg BID of acalabrutinib. All tested dose levels have been well tolerated and, to date, no DLTs have been observed. Robust clinical responses have been observed with dosages as low as 100 mg QD. Preliminary PK data from ACE-CL-001 suggests a plateauing of exposure after 250 mg QD. PD results from this study also show 100 mg BID has the highest BTK occupancy at 24 hours of all the regimens evaluated. Therefore, 100 mg BID maintains full target coverage over 24 hours, while lowering the Cmax and AUC of acalabrutinib suggesting this regimen is preferred when acalabrutinib is being administered with other agents to lower the potential risk of drug-drug interactions. Therefore, based on PK/PD and efficacy results of the Phase 1/2 study, a 200-mg total daily dose, administered 100 mg BID, will be evaluated in this protocol.

Because acalabrutinib has not yet been evaluated in subjects with MF, an adaptive regimen will be used in Part 3. Preliminary data in CLL suggest that responses to acalabrutinib occur rapidly; in study ACE-CL-001, some subjects obtained PRs after only 2 cycles (8 weeks) of therapy. Thus, subjects in Part 3 will receive at least 6 weeks run-in with acalabrutinib alone before beginning combination therapy with pembrolizumab. The adaptive dosing regimen allows for the reasonable possibility that robust activity will be seen in MF using acalabrutinib as a single agent, while providing combination therapy of acalabrutinib plus pembrolizumab for subjects who do not show a clinically meaningful response to acalabrutinib alone. Under Amendment 3 of this protocol, Part 3 is closed to enrollment.

The dose of pembrolizumab planned to be studied in this trial is 200 mg Q3W. The dose recently approved in the United States and several other countries for treatment of melanoma subjects is 2 mg/kg Q3W. Information on the rationale for selecting 200 mg Q3W is summarized below.

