## 3.9 CONCOMITANT THERAPY

## 3.9.1 Permitted Concomitant Therapy

Antiemetics are permitted if clinically indicated. Standard supportive care medications are permitted as per institutional standards.

For subjects considered at risk for tumor lysis syndrome: Administer appropriate hydration and allopurinol or rasburicase per institutional standards before initiating treatment.

For subjects at risk for pneumonitis: In selected subjects (e.g., those with a history of recurrent pneumonias), anti-infectious prevention should be considered. Initiation of antibiotic prophylaxis against pneumocystis infection (e.g., with trimethoprim-sulfamethoxazole, dapsone, aerosolized pentamidine, or atovaquone) beginning before study drug administration may be warranted. Such support may also offer the benefit of reducing the risk for other bacterial infections (Stern 2014). Prophylaxis with IV immunoglobulins (IVIG) may be appropriate in subjects with

low Ig levels (Raanani 2009). Local practices or guidelines regarding infection prophylaxis may be followed.

For subjects at risk for infections: Bacterial/viral/fungal prophylaxis is allowed per institutional standards.

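### When a strong CYP3A inhibitor cannot be avoided beyond a short course, Section 3.10.7 requires only close monitoring, with no acalabrutinib dosing decision and no medical-monitor contact

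*Protocol*

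**What the plan says.** Protocol Section 3.10.7 deals with CYP3A inhibitors in four steps.

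- General rule, at any duration: "the concomitant use of strong inhibitors/inducers of CYP3A (see Appendix 2) should be avoided when possible".
- Short courses: "If a subject requires short-term treatment with a strong or moderate CYP3A inhibitor (such as anti-infectives for up to 7 days), interrupt acalabrutinib treatment".
- Entry: subjects who need an Appendix 2 drug should not be enrolled unless it can be stopped or substituted. Exclusion 15 in Section 3.3.2 also bars them.
- Need arising on study, with no duration given: "If a subject requires a strong CYP3A inhibitor while on study, monitor the subject closely for potential drug-related toxicities".

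Section 3.9.2 covers strong and moderate inhibitors needed on study and tells sites to "follow the acalabrutinib treatment/dosing instructions described in Section 3.10.7 and monitor the subject closely for potential toxicities". Section 3.9.4 does not list strong inhibitors among prohibited therapies; for "additional information on drugs with potential drug-drug interactions, refer to Section 3.10.7" is its only pointer. For strong inducers, by contrast, Section 3.10.7 sets an acalabrutinib dose for the whole co-administration: 200 mg BID, then back to 100 mg BID.

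**The concern.** A brief course of even a moderate inhibitor stops acalabrutinib. A longer course of a strong inhibitor does not by itself require any change to 100 mg BID, or a call to anyone. On its face, the longer and potentially larger overexposure gets the weaker protection.

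The situation is foreseeable. For subjects at risk of infection, Section 3.9.1 says "Bacterial/viral/fungal prophylaxis is allowed per institutional standards", and Appendix 2 lists itraconazole, ketoconazole, posaconazole and voriconazole. That prophylaxis could outlast a short course is my inference; the documents give no frequency or duration.

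At stake is the safety of individual subjects in a study whose primary objective is the safety profile of the combination. The monitoring instruction names no tests and no interval. Under Section 3.0, scheduled visits from Week 127 are 24 weeks apart, and later 52 weeks apart. Under Section 3.6, subjects who stay in the study for drug access after database closure have standard-of-care visits, and only SAEs are reported.

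**Working it through.** There is no design figure to reproduce. The check is a comparison of text, followed by the size of the interaction.

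**Step 1. Is there an action elsewhere for a longer strong-inhibitor course?**

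| Protocol location | What it provides | Action for a longer course? |
|---|---|---|
| 3.10.7, general rule | Avoid when possible | None once use is unavoidable |
| 3.10.7, short-term rule | Interrupt; up to 7 days given as an example | Not if the course is not short-term |
| 3.10.7, on-study sentence | Monitor closely | Monitoring only |
| 3.9.2 | Follow 3.10.7, and monitor | Returns to 3.10.7 |
| 3.9.4 | No prohibition; refers to 3.10.7 | Returns to 3.10.7 |
| 3.3.2, exclusion 15 | Entry bar | Does not cover a need arising later |
| 3.8 and 3.8.1 | Discuss planned delays or modifications with the medical monitor | Does not make an inhibitor a trigger |
| 3.8.1, Table 2 | Hold for listed toxicities; 100 mg QD after the third occurrence | Responds to toxicity, not to co-medication |

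No location states a hold, a dose or a consultation for this case.

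**Step 2. How large is the interaction?** Section 1.4.1 (ACE-HV-001, Part 3) gave a single 50 mg dose with and without itraconazole to 17 subjects. AUC rose 4.9- to 5.1-fold and Cmax 3.7-fold. CL/F was 217 L/h without and 44 L/h with itraconazole. At a fixed dose AUC is inversely proportional to CL/F, so:

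AUC ratio = 217 / 44 = 4.93

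This agrees with the reported AUC range and with the approximate 5-fold figure in Section 3.10.7. It was not measured at 100 mg BID or with any other drug in Appendix 2. That appendix defines a strong inhibitor as one raising the AUC of a CYP3A substrate at least 5-fold.

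**Step 3. Do the dose-ranging data cover that exposure?** Section 3.2 reports on 100 to 400 mg QD and 100 to 200 mg BID: "All tested dose levels have been well tolerated and, to date, no DLTs have been observed".

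- Highest daily dose: 400 mg QD, or 2 × 200 = 400 mg
- Study daily dose: 2 × 100 = 200 mg
- Ratio: 400 / 200 = 2.0

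The same section adds: "Preliminary PK data from ACE-CL-001 suggests a plateauing of exposure after 250 mg QD". The higher-dose cohorts may therefore not have reached even twice the exposure. Itraconazole acts differently, by lowering clearance at a fixed dose. These data neither show nor exclude harm at about 5-fold exposure.

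**Step 4. How is the opposite interaction handled?** Rifampin lowered AUC to 23% (Section 1.4.1, ACE-HV-004), a factor of 1 / 0.23 = 4.3. For an interaction of similar size, the inducer rule gives an explicit dose.

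**The case against.** The best case against the point is that the protocol's silence is reasonable discretion.

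- Avoidance applies at any duration and can be met by changing the other drug or by holding acalabrutinib.
- Seven days is an example, not a cutoff, and short-term is undefined, so a somewhat longer course can still fall under the interruption rule.
- The monitoring sentence is not written as a long-course rule, and Section 3.9.2 makes monitoring additional to the dosing instructions.
- Section 3.8 warns that withholding treatment for only 7 days can transiently worsen disease. Pausing for a short anti-infective is tolerable, but an open-ended pause could in effect end anticancer therapy.
- Backstops exist: toxicity holds, Table 2, medical-monitor discussion of modifications, and withdrawal by investigator decision (Section 3.11).
- Section 1.2.6 sends sites to the Investigator Brochure, which is not available here and may say more.
- Few subjects are likely to be affected. Median exposure was 3.4 months at the September 2017 cutoff (Section 1.4.2.1).

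Most of this stands, and it limits the point. It rules out a mandatory open-ended interruption as the remedy, and it confines the claim to what the protocol text says. It does not supply the missing step. Once avoidance has failed and the course is not short-term, the text requires no dosing decision and no conversation. The backstops act after toxicity appears or after someone has already planned a modification. If longer courses are meant to be a benefit-risk judgement, the protocol should say who makes it and when.

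**Conclusion.** The point holds as a gap in the written safety instructions. For a strong inhibitor that is unavoidable beyond short-term use, Section 3.10.7 asks only for close monitoring. The interaction was about 5-fold with itraconazole, and the same section treats it as reason to interrupt for a short course and not to enroll. A low-cost correction is worth making. Confidence is medium, because the Investigator Brochure has not been seen.

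A reader might infer four stronger things that the documents do not support:

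- **That the protocol deliberately authorizes full dose during long courses.** The monitoring sentence sets no duration, and avoidance remains the default. The fault is a missing decision step.
- **That subjects have been harmed.** No case, frequency or duration of strong-inhibitor use is given, and the 5-fold figure comes from single doses in 17 subjects.
- **That the safety results are compromised.** No endpoint, decision rule or SAP analysis depends on this instruction.
- **That acalabrutinib must always be stopped.** The warning in Section 3.8 makes that a trade-off for each subject.

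Enrollment closed in May 2017 with 161 evaluable subjects (Section 5.1). The number still on acalabrutinib is not given and is probably small.

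**What to change.** Replace the on-study monitoring sentence in Section 3.10.7, which ends the paragraph on enrollment of subjects needing Appendix 2 drugs, with text such as:

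> *When a strong CYP3A inhibitor is needed on study beyond short-term use, substitute a drug that is not a strong CYP3A inhibitor where possible. If this is not possible, contact the medical monitor before co-administration to agree whether to hold, reduce or continue acalabrutinib and the monitoring schedule, weighing the risk of disease worsening on interruption (Section 3.8). The short-term interruption rule above is unchanged.*

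The undefined boundary of short-term then matters less, because a strong inhibitor on either side of it leads to an action.

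Cost: one sentence in the next amendment or a site letter, with no new data. The downside is a medical-monitor contact per case and possible treatment interruption in a few subjects.

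Three further changes are not needed. An open-ended mandatory interruption would override the judgement that Section 3.8 calls for. A cross-reference in Section 3.9.1 would add little, since Section 3.9.2 follows directly and already covers inhibitors needed on study. A separate listing of adverse events during overlap is not required: the SAP already summarizes concomitant medications (9.5.2) and lists adverse events by subject (9.7.1).
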